- Randomize half of the study participants (50%) to view a 9-minute informational video explaining that life expectancy in their area has substantially increased since 2003 and that this gain can primarily be attributed to reduced HIV-related mortality because of increased access to treatment. The other half of study participants will be randomized 1:1 to an attention placebo control video (25%) and a pure control arm (25%).
- Conduct immediate post-video survey and assess uptake of job skills workshop, HIV testing voucher, condom offer, and a savings device
- Assess uptake of HIV testing during the home-based AHRI surveillance visit, which occurs about 6 weeks after the baseline survey
- Conduct follow-up survey at 8 weeks to measure changes produced by the video in survival expectations and health behaviors, and
- Assess longer run effects on linkage to care as well as other schooling and employment behaviors observed in the surveillance

The primary endpoint is an index of all human capital investment behaviors including use of the HIV testing voucher, uptake of HIV testing in the surveillance visit, participation in a job-skills workshop, and use of the savings device.

A6. Study Population and Inclusion Criteria

The proposed study will investigate survival expectations and health behaviors among young adults residing in the AHRI surveillance who are ages 18 to 25.

Inclusion criteria

- Member of a household that participates in the AHRI population surveillance (i.e. not a visitor to the area)
- Resided in the AHRI surveillance area in the previous year (and was therefore included in the population listing that formed the sampling frame) and was still residing in that location when the first contact attempt was made
- Resides in one of the specific AHRI week-blocks that we sampled from for the study (further details below)
- Ages 18-25 years

Exclusion criteria

- <18 years at time of baseline interview
- >25 years at time of baseline interview
- Not able to provide consent
- Did not consent to participate

A7. Sampling Strategy and Sample Size Determination

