Definition: Participants will be offered the opportunity to test for HIV via a household visit by the AHRI surveillance team 4-6 weeks after the baseline survey. By linking with the AHRI surveillance, we will assess whether individuals tested in the AHRI home visit. All those who tested will be coded as 1; all others, including those who were not at home will be coded as 0.

[Time Frame: 1 month]

Use of clinical HIV services

Definition: For individuals who are HIV-infected, the intervention could increase linkage to care and retention on HIV treatment. We will assess use of clinical HIV services as a binary indicator for whether the individual sought care in the public sector HIV care and treatment program in the three months after baseline. Clinical data from the public sector HIV treatment program are routinely linked into the population surveillance platform by AHRI data management.

[Time Frame: 3 months]

Self-reported behaviors

Change in time allocated to education or labor supply

Definition: At both baseline (pre-intervention) and 2-months follow-up, we ask respondents to report hours spent on different activities in the last week. These questions were adapted from the Malawi Living Standards Measurement Survey, Module E (p17). We will assess change in the total hours spent on the following activities (aggregating time spent across these activities):

- a household business
- formal work for pay
- informal work for pay
- apprenticeship/internship
- looking for work
- schooling
- job training

(The activities that we measured but excluded from this list are: housework, caregiving, socializing with friends, doing nothing, and sleep)

[Time Frame: 2 months]

Change in self-reported savings

Definition: Difference between baseline and 2-month follow up in response to the following question: how much have you saved in bank accounts, at home, or elsewhere?

[Time Frame: 2 months]

Change in self-reported non-HIV health risk behaviors

Definition: We will assess changes between baseline and 2-month follow-up in self-reported health risk behaviors. We will conduct statistical testing on an additive index of the following: any smoking in the last week; any drinking in the last week; any heavy drinking (3+ drinks) in the last week; does not always use a seatbelt. Range of this index will be 0 to 4.

[Time Frame: 2 months]

Change in self-reported unprotected sexual activity

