Definition: We will assess changes between baseline and 2-month follow-up in self-reported unprotected sex. Specifically, we will assess number of times a person reported having condomless sex in the last 30 days.

[Time Frame: 2 months]

Change in self-reported current HIV care-seeking

Definition: We will assess change between baseline and 2-month follow-up in a combined self-report measure of whether the respondent either tested for HIV within the last 3 months and whether the respondent is currently taking ARVs.

[Time Frame: 2 months]

Employment, education, and care-seeking outcomes in the AHRI surveillance

Definition: We will assess longer run education, employment, migration, and care-seeking outcomes observed through household proxy report and clinic linkage in the AHRI population-based surveillance platform. Specifically, we will assess whether the respondent is reported to be in school, working, looking for work, or none of the above; whether the respondent is still residing in the surveillance area; and whether the respondent has linked to clinical HIV services.

[Time Frame: 1 year, 2 years]

Attitudes and beliefs

Change in beliefs about life expectancy in the community

Definition: at baseline and at 2-month follow-up, we ask people to consider 20 people their age and gender in the community and to estimate how many they think will be alive at age 30, 40, ... 80. We will construct a measure of perceived community life expectancy by linearly interpolating the responses to these questions (starting at the respondent's age) and computing the area under the curve. This value is the average number of years they expect a demographically similar person in the community to live.

[Time Frame: 2 months]

Change in beliefs about lifetime risk of HIV infection

Definition: change between baseline and 2-month follow-up in the subjective probability (out of 20) of becoming HIV-infected at some point in their life. Although we do not expect that the video will change underlying beliefs about HIV risk; it could change people's willingness to consider these risks, which would be important to know in interpreting our results.

[Time Frame: 2 months]

Change in beliefs about work and schooling

Definition: At baseline and 2-month follow-up we asked respondents about the chances (out of 20) that they would complete different levels of schooling and about the chances they would be employed in the future. We will assess changes in these beliefs.

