We will additionally assess balance on all primary and secondary outcomes described above that are measured at baseline.

Through linkage to the AHRI surveillance, we will additionally assess balance on: whether the person has a child; household size; distance to the nearest clinic, whether anyone in the household died from HIV in the prior 10 years; whether anyone in the household is receiving public sector ART at time of baseline.

For each baseline covariate, we will report a t-test for the null hypothesis of equal means in Arm 1 vs. Arms 2+3 (pooled).

B4. Statistical analysis of treatment effects

All statistical analyses will involve comparisons across the treatment arms described above. For each outcome, we will generate the following data:

Example Results Table (fake data)

	Sample Means				Treatment Effect Estimate (95% CI)		
	Arm 1, n=XXX	Arms 2+3, n=XXX	Arm 2, n=xxx	Arm 3, n=xxx	Crude difference	Adjusted for design variables ^a	Adjusted for design, strong predictors, and baseline imbalance ^b
Outcome 1	1.2	1.5			-0.3 (-0.5 to 0.2)	-0.3 (-0.5 to 0.2)	-0.3 (-0.5 to 0.2)
			1.7		-0.5 (-0.8 to 0.0)*	-0.5 (-0.7 to 0.0)*	-0.5 (-0.7 to 0.0)*
				1.4	-0.3 (-0.5 to 0.3)	-0.3 (-0.5 to 0.2)	-0.3 (-0.5 to 0.2)
Outcome 2							
...							
Outcome k							

^aDesign variables are those variables on which balance was explicitly assessed during randomization. ^bStrong predictors of the outcome are those factors in the baseline balance table that are adjusted differences include regression adjustment for stratifying variables, variables used in the constrained randomization, and variables that were not balanced at baseline despite randomization (p-value <0.1 in F-test).

Sample means will be reported for Arm 1, the combined control (Arms 2+3), and for Arm 2 and 3 separately. When assessing changes from baseline to follow-up, we will simply define the outcomes as within-subject “differences” to facilitate comparisons with other outcomes observed only after the intervention.

Crude comparisons of outcomes between treated and comparison arms will be assessed in linear regression models, regressing the outcome on an indicator for treatment arm and indicators for week-block, a stratification variable. We will adjust our standard errors for clustering at the household level, given that error terms without households may be correlated.

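### The secondary outcome on use of clinical HIV services merges new linkage, retention and continuing care, and ignores the participant's own care before baseline

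*Combined protocol and SAP*

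**What the plan says.** Under *Use of clinical HIV services*, B1.2 opens with its target group, "For individuals who are HIV-infected", and says that "the intervention could increase linkage to care and retention on HIV treatment". It then defines a single "binary indicator for whether the individual sought care in the public sector HIV care and treatment program in the three months after baseline". The definition sets no condition on care before baseline, is not a change from baseline, and does not say whether the denominator is all participants or only those who are HIV-positive. The source is the routine clinic linkage: "Clinical data from the public sector HIV treatment program are routinely linked into the population surveillance platform".

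The longer-run item in B1.2 (1 and 2 years) records "whether the respondent has linked to clinical HIV services", with no restriction to people not yet linked at baseline. A5 lists the matching study component: "Assess longer run effects on linkage to care as well as other schooling and employment behaviors observed in the surveillance".

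Three other parts of the plan bear on this:
- B3 checks balance on "whether anyone in the household is receiving public sector ART at time of baseline", a household-level item, and on outcomes measured at baseline.
- B4 always adjusts for the randomisation variables, including HIV-positive and HIV-negative status. Three named predictors are also included, none of them care status. Any other baseline variable enters only if its balance test gives p<0.1.
- A separate B1.2 outcome is a change in self-reported care-seeking. It combines recent testing with "whether the respondent is currently taking ARVs".

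**The concern.** Three kinds of people score 1: someone newly linked after the video, someone in care who might have lapsed but did not, and someone in care who would have attended anyway. The first two are the effects the plan names. The third carries no information about the video, and the indicator cannot tell the three apart.

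Three things follow. A linkage effect is spread over a group that includes people who cannot newly link. The number already in care differs between arms by chance, and that difference feeds straight into the outcome. And a positive result could not be read as linkage, which A5 names.

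The unstated denominator adds a further choice. Restricting to people known to be HIV-positive before baseline drops those of unknown status, who could newly link. Defining the group by tests after the video would make membership depend on testing, which the video is meant to change. The documents do not say that such tests will be used, but they leave it open.

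**Working it through.** **The plan's own figure.** No power is stated for this outcome. The general figure in A7 reproduces: with 225 vs 225, 80% power and two-sided 5% (assumed), the detectable difference is (1.960 + 0.842) × √(2/225) = 0.264 SD, against the stated 0.26. Nothing here disputes it.

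**Inputs.** The documents give the target of 450, the 1:1 split of Arm 1 against Arms 2+3, and HIV prevalence of one third among all adults (A3). They give no prevalence for ages 18–25, share already in care, attendance rate or linkage rate. Everything else below is assumed.

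**1. Dilution.** Let c be the share of HIV-positive participants already in care, r their chance of a visit in the window, and l0 and l1 the linkage rates among the rest. The expected indicator is c·r + (1−c)·l. With r equal in both arms, the difference is (1−c)(l1−l0). A 10-point linkage effect becomes 7, 5 or 3 points at c = 30%, 50% or 70%. It reaches zero only if c = 1.

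**2. Attribution.** Take c = 50%, r = 80%, l = 10%:
- No effect: 0.5×0.80 + 0.5×0.10 = 45%.
- Linkage alone, 10% to 20%: 0.5×0.80 + 0.5×0.20 = 50%.
- Retention alone, 80% to 90%: 0.5×0.90 + 0.5×0.10 = 50%.

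The last two are identical on this outcome.

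**3. Noise from prior care.** Assume 45 HIV-positive participants, 27 in care (95% attend) and 18 not (linkage 20% vs 40%).
- Among the 45: (27×0.95 + 18×0.20)/45 = 65.0% vs (27×0.95 + 18×0.40)/45 = 73.0%, an 8-point difference.
- With 22.5 per arm, the chance difference between arms in the share in care has SD √(2×0.6×0.4/22.5) = 14.6 points. Multiplied by the 75-point gap in visit rates (95% − 20%), that is about 11 points, more than the 8-point signal.
- Over all 450, the control-arm variance is 0.065×0.935 = 0.0608. Adjusting for HIV status, if every infection were already known, leaves 0.10×0.65×0.35 = 0.0228. Adding prior care leaves 0.06×0.95×0.05 + 0.04×0.20×0.80 = 0.0093. So HIV status helps, and prior care removes about 59% of what is left (1 − 0.0093/0.0228).

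**4. Power with the split, on matching denominators.** Power = Φ(d/SE − 1.96) + Φ(−d/SE − 1.96), with SE = √[p0(1−p0)/n + p1(1−p1)/n]; unadjusted and without clustering.

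In the step 3 scenario:
- As defined, all 450: 29.25/450 = 6.5% vs 32.85/450 = 7.3%; d = 0.80 points, SE 2.39, power about 6%.
- New linkage among the 450 − 27 = 423 without prior care: 3.6/423 = 0.85% vs 7.2/423 = 1.70%; d = 0.85 points, SE 1.09, power about 12%.

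With prevalence one third, c = 50%, r = 90% and linkage 10% vs 40%:
- As defined: 16.7% vs 21.7%, n = 225 per arm, SE 3.70, power about 27%.
- Without prior care: 2.0% vs 8.0%, n = 225 − 37.5 = 187.5 per arm, SE 2.23, power about 77%.

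Ranges at r = 90%, prevalence 10% or 33% and c = 30%, 50% or 70%:

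| Linkage among those not in care | As defined, all participants | Without prior care |
|---|---|---|
| 10% vs 20% | 5–12% | 8–27% |
| 10% vs 40% | 7–56% | 20–90% |

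Event counts are small in many of these cells, so the normal approximation is rough.

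**The case against.** A reader might infer that people already in care score 1 whatever their arm, so that the outcome cannot show linkage at all. The documents do not support that. A person in care who makes no visit in the three months scores 0, and that is how retention, the second stated aim, is captured. People not in care can move from 0 to 1. Randomisation balances prior care in expectation, so a chance imbalance is noise and not bias.

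A reader might also infer from step 3 that the definition loses 60% of the effect (8 points instead of 20). That compares 45 HIV-positive people with the 18 of them not in care. A rule that avoids conditioning on later test results must analyse everyone without prior care, and there the difference is 0.85 against 0.80 points. The gain comes mainly from lower variance.

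The plan also has partial safeguards. Randomisation was constrained on HIV-positive status, and the adjusted models include it. Household ART and the self-reported care-seeking measure can be checked for balance. That measure is itself a change score including current ARV use. These points stand, but they do not close the gap. HIV status is not care status, household ART is not the participant's own care, the self-report measure mixes testing with treatment, and adjustment for these last two depends on p<0.1.

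Finally, this is one of many secondary outcomes in a pilot that A7 says is powered only for large effects. That limits how much the point matters, but does not remove it.

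**Conclusion.** The point holds as one of dilution, noise and attribution. The indicator merges the two effects the plan names with ordinary continuing care, and nothing in B3 or B4 reliably separates them. The 1- and 2-year linkage item has the same gap for people linked before baseline. The comparison between arms stays valid, and no primary outcome is affected.

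The size cannot be fixed from the documents. The diluting factor among HIV-positive participants is 1−c, and c is not given. Separating prior care raises power in every scenario tried, from a trivial gain (6% to 12%) to a material one (27% to 77%), but for modest linkage effects power stays low either way. The power figures assume that the video has no effect on attendance among people already in care. Attribution does not depend on those inputs: without prior care status, a difference on this outcome cannot be assigned to linkage or to retention.

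**What to change.** Use the linked clinic records to classify each participant by own public-sector HIV care before baseline, with a look-back window written down before unblinding. The documents do not point to a particular length. Then:
- Keep the overall indicator, state its denominator, and adjust it for prior care whatever the balance test shows.
- Report (a) new linkage: a first visit after baseline among all participants with no prior care, without conditioning on test results obtained after the video.
- Report (b) retention: a visit in the three-month window among participants in care before baseline.
- Apply (a) to the 1- and 2-year linkage item.

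The cost is some plan wording and one pre-baseline variable from a linkage already being made. The data managers need to confirm that individual visit histories reach back far enough, because B3 shows only household ART status at baseline. The drawback is that retention rests on a small group and new linkage on few events, each with low power, so both should be labelled secondary and descriptive. A12 schedules unblinding for the day after the plan is posted. If it has already happened, the split should be reported as added afterwards.

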Definition: Subjective life expectancy is defined as the area under the subjective survival curve. Respondents will be asked about the chances of surviving to age 30, 40, ..., 80 years. We will linearly interpolate the responses beginning at their current age and ending at 80 years. We will then calculate the area under this curve, which we define as subjective life expectancy (number of years expected to live between current age and age 80). Our primary outcome for beliefs will be the change in subjective life expectancy between baseline (pre-intervention) and follow-up (at 2 months). We will also assess change in subjective life expectancy between baseline and immediate post-intervention assessment as a secondary outcome.

[Time Frame: 2 months]

4. Positive attitudes towards HIV and HIV treatment (at 2 months)

Definition: Immediately after the intervention and at 2 months, we ask participants whether they strongly disagree, disagree, agree, or strongly agree with a series of statements regarding attitudes towards HIV and HIV treatment. As a primary outcome, we will assess differences in a composite index of 12 of these measures, comparing attitudes between treatment arms at 2 months. We will assign points (1=strongly disagree, 2=disagree, 3=agree, 4=strongly agree) based on responses, we will sum over the following items, and we will construct a z-score based on the mean and standard deviation in the baseline data. "Reverse code" denotes that the variable will be scored (4=strongly disagree, 3=disagree, 2=agree, 1=strongly agree). We will also assess differences immediately after the intervention as a

secondary outcome. Note: the attitudes questions are asked after the intervention. There is no baseline.
 [Time Frame: 2 months]

ITEM	REVERSE CODE?
If I were HIV infected, I could have children and a family	
If I were HIV infected, it would be difficult to find a romantic partner	X
If I were HIV infected, I could still do all the activities I enjoy	
If I were HIV infected, it would make it harder to get and keep a job	X
If I were HIV infected, it would change my career plans	X
If I were HIV infected, I could expect to live to pension age (age 60)	
If I were HIV infected, I could expect to live long enough to see my children grow up and to meet my grandchildren	
I am scared to find out my HIV status	X
If I were HIV infected, it would be hard to start ARVs (HIV treatment)	X

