Adjusted effect estimates. We will estimate adjusted effect estimates in multivariate linear regression models. Adjustment for covariates in an RCT has three aims[23]:

- (design variables) to obtain appropriate standard errors when conducting stratified or constrained randomization;
- (strong predictors of the outcome) to reduce residual variance in the outcome, leading to smaller standard errors and narrower confidence intervals; and
- (factors with strong baseline imbalance) to eliminate the impact of any imbalances on observed baseline factors, despite randomization

(a) In our adjusted analyses, we will include the following design variables:

- Stratification variables: week block
- Constrained randomization variables: sex, age, whether the person was in school, orphan status, HIV positive status, HIV negative status (unknown is the third category), and household asset quintile

(b) We will include the following variables believed *a priori* to be strong predictors of HIV testing and human capital investment:

- Distance to nearest clinic
- Baseline subjective life expectancy
- Baseline beliefs about lifetime HIV infection risk

(c) Finally, to eliminate imbalances on observables, we will adjust for variables with $p < 0.1$ for the t-test of differences between Arm 1 and Arm 2+3.

B5. Subgroup analyses

The informational intervention is expected to have the greatest impact for individuals with low baseline survival beliefs and for individuals with high baseline beliefs about lifetime chances of contracting HIV.

Perceived likelihood of lifetime HIV infection. The impact of the informational video is likely to vary by baseline perceived risk of lifetime HIV infection. We will assess for linear effect modification of our primary outcomes by perceived lifetime infection risk.

Baseline survival expectations. The impact of the informational video is likely to vary by baseline survival expectations, with the greatest potential shift in beliefs for individuals with previously low survival expectations. We will assess for linear effect modification of our primary outcomes by baseline subjective life expectancy.

Finally, we will assess effect modification by age (continuous, 18-25) and sex of the respondent (M/F).

B6. Robustness checks

We will subject our primary results (Arm 1 vs. Arms 2+3 for primary outcomes) to robustness checks.

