Logistic regression model. We will also estimate our primary models using multivariate logistic regression to assess sensitivity to specification. In lieu of odds ratios, we will report marginal effects associated with the treatment arm, to enable comparison with the estimate from the OLS models. Again, standard errors will be clustered at the household level.

Restrict to HIV-uninfected. HIV testing uptake – one of our primary outcomes – is less relevant for individuals who already know their current HIV status. In a robustness check, we will assess HIV uptake after excluding: individuals who reported that they had ever tested for HIV and were certain that they were HIV positive at baseline (20 out of 20 beans); and individuals who reported testing for

HIV in the prior 3 months and reported that they were sure that they were HIV negative (0 out of 20 beans).

Remove participants with inconsistent answers and extreme outliers. A small number of participants reported inconsistent answers to the survival expectations questions at baseline. We will assess robustness of results after removing: participants who reported non-zero chances of survival at ages greater than the “oldest possible age” they could imagine living to; participants who reported that it was unlikely they would live to 60 years but allocated >10 beans; participants who reported that it was likely they would live to 60 years but allocated <10 beans. Demographic differences between persons with consistent and inconsistent answers will be reported.

B7. Adjusting Inference for Multiple Hypothesis Testing

No adjustments will be made for our primary outcomes.

For secondary outcomes, the primary manner in which we adjust for multiple hypotheses being tested is by grouping outcomes into indices such that their joint significance will be tested. If we do not find that there is overall significance for aggregated measures of behaviors such as local of control, we will not move test statistical significance of individual index components. In addition, for families of outcomes where we are interested in testing the treatment effect both for an index overall as well as individual components, when the number of tests is large (greater than 10), we adjust our standard errors using the Benjamini-Hochberg procedure[24] for controlling the false discovery rate to less than 0.05.

B7. Handling attrition

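### B4 reports three models per outcome and names none as primary, and it fixes the outcome's own baseline as a covariate for only 2 of 14 change outcomes

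*Combined protocol and SAP*

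**What the plan says.** The example results table in B4 has three effect columns for each outcome: crude (arm and week-block), adjusted for the design variables, and adjusted for design variables, strong predictors and baseline imbalance. B2 and the opening of B6 call the comparison of Arm 1 with Arms 2+3 primary. Neither says which column is primary. B6 then promises: "We will also estimate our primary models using multivariate logistic regression to assess sensitivity to specification".

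B4 builds the adjusted analyses from three sets:
- **(a)** week block and the constrained-randomization variables.
- **(b)** distance to clinic, baseline subjective life expectancy and baseline lifetime HIV risk, chosen as believed "to be strong predictors of HIV testing and human capital investment".
- **(c)** a screened set: "to eliminate imbalances on observables, we will adjust for variables with" p<0.1 in the balance t-test.

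B3 makes the pool for (c) wide: "We will additionally assess balance on all primary and secondary outcomes described above that are measured at baseline". Footnote b to the table describes the third column differently, cites an F-test, and loses its thread: "predictors of the outcome are those factors in the baseline balance table that are adjusted differences include regression adjustment".

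For change outcomes B4 says "When assessing changes from baseline to follow-up, we will simply define the outcomes as within-subject" differences, so that they compare easily with outcomes seen only after the intervention. One stated aim of adjustment is "to reduce residual variance in the outcome, leading to smaller standard errors and narrower confidence intervals".

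**The concern.** There are two separate points.

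**No primary model.** When the three columns disagree, no rule says which one is the result. No multiplicity adjustment is planned for the four primary outcomes, so nothing else limits the choice. The plan's own gates also need a single model. B1.2 and the multiplicity section allow tests of index components only if the index is significant, without saying in which column. The third column cannot be written down before the balance tests are run.

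**Own baseline left to a screen.** A raw change score is a valid outcome, but it is usually less precise than the same outcome adjusted for its own baseline. Most of the change outcomes get that adjustment only in the third column, and only if the arms happen to differ at p<0.1. Precision is then gained or lost by chance.

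**Working it through.** **1. The plan's own figure.** A7 gives N=450, 80% power and 0.26 SD. Two-sided 5% is assumed from the 95% intervals in B4, and 1:1 allocation gives 225 per arm. The detectable difference is (1.960+0.842)×√(2/225) = 0.264 SD, and power at 0.26 SD is 78.7%. Example 1 (4 years, SD 15) gives 80.7%. The sample size reproduces and is not in dispute.

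**2. Count of change outcomes.** There is one primary (subjective life expectancy). There are 13 secondary headings: time allocation, savings, non-HIV risk behaviors, unprotected sex, HIV care-seeking, community life expectancy, lifetime HIV risk, work and schooling beliefs, future orientation, locus of control, health locus of control, life satisfaction and mental health. The total is 14. Set (b) contains the own baseline for two, subjective life expectancy and lifetime HIV risk, and only in the third column. The other 14−2 = 12 depend on the screen.

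**3. Candidates for set (c).** These 12 baselines, plus four linked variables in B3 that are not in (a) or (b) (has a child, household size, household HIV death, household ART), make at least 16. By chance alone 16×0.1 = 1.6 enter. The probability of at least one is 1−0.9^16 = 81% if they are independent.

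**4. False-positive rate if any column counts.** Null trials were simulated with 225 per arm, without clustering or week-block terms.

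For HIV testing, the composite and attitudes, the simulation used a normal outcome, 7 covariates in (a), 3 in (b), 16 screened, and 12,000 trials per cell:

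| Total covariate R² (assumed) | 0.05 | 0.10 | 0.20 | 0.30 |
|---|---|---|---|---|
| Any of three significant | 6.6% | 7.1% | 7.8% | 8.2% |
| Same, constrained randomization simulated | 6.5% | 6.8% | 7.1% | 8.1% |

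Each model alone gives 4.7–5.2%. With R² spread evenly over all 26 covariates the figures are 6.1/6.5/7.4/7.6%. For a binary outcome with 30% uptake (assumed) they are 6.0% and 6.3% at latent R² 0.05 and 0.10.

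For change in subjective life expectancy, where the first two columns are raw change and the third contains the own baseline, with ρ the baseline to follow-up correlation:

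| ρ (assumed) | 0.3 | 0.5 | 0.7 | 0.8 |
|---|---|---|---|---|
| Raw or own-baseline adjusted (60,000 trials) | 7.8% | 7.4% | 6.9% | 6.3% |
| Any of three, design covariates added (6,000 trials) | 8.7% | 7.5% | 7.0% | not run |

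**5. Precision of raw change.** With equal SD σ at both visits, Var(change) = 2σ²(1−ρ) and Var(baseline-adjusted) = σ²(1−ρ²), so the ratio is 2/(1+ρ).

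| ρ (assumed) | 0.3 | 0.5 | 0.7 | 0.8 |
|---|---|---|---|---|
| Variance ratio | 1.54 | 1.33 | 1.18 | 1.11 |
| Raw-change interval wider by | 24% | 15% | 8% | 5% |

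The 12 secondary outcomes carry no power claim. Power is therefore shown only for Example 1 in A7 (4 years, SD 15), where it measures what the choice of column is worth for the primary belief outcome. At ρ = 0.3/0.5/0.7 the SD of the change is 15√(2(1−ρ)) = 17.75/15.00/11.62, and the adjusted SD is 15√(1−ρ²) = 14.31/12.99/10.71. Power at 225 per arm is 66.7/80.7/95.5% raw and 84.3/90.4/97.7% adjusted. At 180 per arm (20% lost) it is 57.1/71.6/90.4% and 75.6/83.2/94.3%.

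**6. Effect of the screen on the 12 secondaries.** The screen admits the own baseline in 9.9–10.0% of null trials. The screened test alone has size 3.7–4.5%, and raw-or-screened gives 5.1–5.3%. The screen costs precision and hardly affects error control.

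**7. Is the dependent variable affected?** No. If Y−B = α + τ·arm + γB, then Y = α + τ·arm + (γ+1)B. The arm effect τ is the same for change and for follow-up value, and a numerical check agreed.

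**The case against.** The case against has force on several points.

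- **All three columns are promised.** A reader will see any disagreement, and nothing in the plan says that one significant column is enough. This stands: the 6 to 9% is a worst case. But no rule excludes that reading, and the index gates still need one column.
- **The text leans toward adjustment.** B4 labels the first column crude, says that design variables are needed for correct standard errors, and B6 speaks of a multivariate model. This narrows the ambiguity but does not settle which of the two adjusted columns is meant.
- **The change-score point is not an error.** Raw change is unbiased, B4 gives a reason for it, the one primary change outcome has its baseline in (b), and A7 says the pilot can detect only large effects. All of this stands. The second point is an improvement in precision and should be read as such.
- **Footnote b may have held a wider rule.** It breaks off, and the cause cannot be told from the text. The count of 2 of 14 rests on the explicit list in B4. As posted, the footnote supplies no usable alternative.
- **Normal, equal-SD formulas fit some outcomes poorly**, such as the 0–4 risk index and the count of condomless sex. This stands, and the precision figures are approximate for them.

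**Conclusion.** Both points hold on the text. The first is the more important: four primary outcomes have three models each and no stated primary model, and the third is fixed only after balance testing. If any column could count, the error rate is about 6 to 9% instead of 5%, depending on assumed R² and ρ.

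The second affects 12 secondary outcomes. It brings no bias and almost no false-positive cost, but intervals are roughly 5 to 24% wider at ρ from 0.8 to 0.3. That gain assumes equal SDs, no household clustering and no other covariates. Sets (a) and (b) may already carry some of the same information, so it is probably an upper bound.

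The plan should be changed, but nothing here invalidates the design. Confidence in the sizes is moderate, because the documents give neither R² nor ρ.

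**What to change.** In B4:

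1. Name one primary model for all outcomes: arm, sets (a) and (b), and the outcome's own baseline as a fixed covariate wherever it is measured. HIV testing and the composite have no matching baseline. For attitudes the plan says so itself: "the attitudes questions are asked after the intervention. There is no baseline". These three use (a) and (b) only.
2. Keep the change as the dependent variable, which preserves the comparability B4 wants. Where a heading covers several items (work and schooling beliefs, life satisfaction), each item uses its own baseline.
3. Label the crude and design-only columns as descriptive. Keep the p<0.1 adjustment in (c) as a sensitivity analysis, since B3 notes that balance among those actually recruited is not known in advance.
4. State that the list in B4 governs over footnote b, complete or delete the footnote, and settle on the t-test or the F-test. Make the reference to primary models in B6, and the index gates, point to the named model.

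The cost is wording in B4, footnote b and B6, and one degree of freedom per change outcome. The baselines are already collected, since the change scores need them. A12 schedules unblinding for the day after posting. If assignments are already known, date the change and report it beside the three models as posted.
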